We will recruit 30 subjects from our Comprehensive Epilepsy Center and through referrals from other clinicians. The patients may be initially informed on of several ways:

- The investigator will briefly explain this study to them, and ask if they would like to hear more about it.
- The potential subject may be approached at the time of a clinic appointment. At that time, the investigator may briefly explain the study.
- The potential subject may receive a telephone call from an investigator on this study. At the time of the telephone call, the investigator may briefly explain the study.

In either case, a “voided copy” of the consent form will be mailed to the potential subject, or handed to them in person if possible. This will allow adequate time to read the consent form in detail, record questions, and consider the option of enrollment.

At the time of consent, randomization will occur based on order of enrollment into the study using a computer-generated randomization table. Subjects will be randomized into three treatment groups. In Group 1, we will target continuous low frequency rTMS (1 Hz, at 95% resting motor threshold (RMT), over ten daily 30-minute sessions) to cortical regions that are highly correlated with the epileptogenic MTL. In Group 2, we will target high-frequency rTMS (10 Hz, 110% RMT, over ten daily 30-minute sessions) to cortical regions that are highly anti-correlated with the epileptogenic MTL. Group 3 will receive sham TMS as a control intervention (using a sham coil over a highly correlated cortical region, over ten daily 30-minute sessions).

Subjects will be blinded to their treatment group assignment. Subjects and family members or caregivers will be asked to maintain diaries of all seizures and possible adverse effects, which will be reviewed by an investigator blinded to treatment group assignments.

1. MRI scanning and data analysis (One hour to complete, on one day)

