EEG recording of interictal epileptiform discharge (IED) frequency will occur 12 weeks after the last rTMS session. **Subject time: 1 hour.**

At 12-week follow-up, the primary outcome measure will be seizure frequency compared to baseline, and the secondary outcome measure will be IED frequency compared to baseline. Subjects will be blinded to their group assignment, as will the investigator who reviews seizure diaries and determines IED frequency on EEG. Adverse events will be tracked closely throughout the study protocol.

Follow-Up

The investigators will conduct a controlled assessment of the response to the initially chosen rTMS protocol and determine if the subject may be appropriate for further rTMS. Investigators may invite subjects back to repeat the study procedures 2-7. The follow-up rTMS protocol chosen by investigators will depend on the subject's response, or lack thereof, to the previously performed protocol.

Subjects who are invited back for further rTMS sessions and choose to return will undergo the following specific procedures:

1. Baseline seizure diary (12 weeks)

Subjects will keep a baseline seizure diary for 12 weeks, during which time connectivity analyses and tMS target creation will be performed by the investigators. **Subject time: 12 weeks.**

2. Pre-rTMS EEG (One hour to complete, on one day)

EEG recording of interictal epileptiform discharge (IED) frequency will occur prior to first TMS session. **Subject time: 1 hour.**

3. Experimental Design for rTMS (On average one and a half hours to complete, on ten consecutive weekdays)

Based on analyses of the subject's response to the initially assigned rTMS protocol, the alternative protocol (either low-frequency rTMS to cortical regions that are highly correlated with the epileptogenic MTL or high-frequency rTMS to cortical regions that are highly anti-correlated with the epileptogenic MTL) will be used. Each subject will have ten 30 minute rTMS sessions over a two-week period, ten consecutive weekdays. **Subject time: 1.5 hours per rTMS session. 10 rTMS sessions.**

4. Post-rTMS EEG (One hour to complete, on one day)

EEG recording of interictal epileptiform discharge (IED) frequency will occur after the last TMS session. **Subject time: 1 hour.**

5. Follow-up seizure diary (12 weeks)

Subjects will keep a follow-up seizure diary for 12 weeks post rTMS. **Subject time: 12 weeks.**

6. Final EEG (One hour to complete, on one day)

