We expect to downmodulate the excitability of the epileptogenic MTL, thus reducing seizure and IED frequency. Although it is difficult to predict the magnitude of such an effect given the unique nature of our targeting based on connectivity findings, prior rTMS studies in epilepsy have shown seizure frequency reductions in the 53-80% range, durable over at least eight weeks of follow-up, and IED frequency reductions in the 14-66% range.^{4,5} Our use of EEG recordings immediately pre- and post-rTMS, as well as at the end of the follow-up period, will allow for an estimation of immediate and delayed/durable effects on the epileptic state in these patients. We expect our results to prove the principle that patients with deep seizure foci can be safely treated by targeting accessible cortical regions and to provide guidance on which active rTMS protocol (high- or low-frequency) is optimal for MTLE.

Our analysis following the second rTMS protocol, in those subjects who participate in that portion of the study, will provide further evidence of the relative efficacy of the two rTMS protocols in downmodulating cortical excitability.

Brain image acquisition

Anatomical and functional connectivity MR images will be acquired using a dedicated research 3.0-Tesla magnet (General Electric Signa VH/i, GE Healthcare, Waukesha, WI) with a commercial head coil. Highresolution structural whole-brain images will be acquired using a T1-weighted sequence with 128 slices per slab, a 256 x 256 matrix, a field of view (FOV) of 256 mm, a slice thickness of 1.33 mm with 0.63 mm interslice gap, repetition time (TR) of 2530 ms, inversion time of 1100 ms, echo time (TE) of 3.39 ms, and flip angle of 7 degrees. Resting-state functional image acquisition will be performed while subjects are asked to rest quietly (acquisition time 6.4 min), using an echo-planar sequence sensitive to BOLD contrast with TR 6000 ms, TE 30 ms, FOV 256 mm, voxel size 2.0 x 2.0 x 2.0 mm, and flip angle 90 degrees.

Functional connectivity analysis

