All subjects will be between 18 and 64 years old and have a diagnosis of MTLE based on the combination of clinical semiology, neuroimaging findings, and EEG results. Subjects with ≥ 1 seizure with loss of awareness per 4-week period, on average, despite the use of antiepileptic drugs (AEDs), will be eligible. AEDs will not be adjusted during the study period, except in compelling clinical circumstances. Exclusion criteria are: 1) prior brain surgery or exposure to TMS; 2) rapidly progressive brain lesions (but low-grade gliomas, cystic lesions, mesial temporal sclerosis, or other static or slowly progressive lesions would be eligible); and 3) inability to tolerate MRI or TMS, or

specific MRI or TMS contraindication as set forth in standard protocols of our institution. Women of childbearing potential will be asked if they may be pregnant, questioned about the use of contraceptives if they are sexually active, and asked to identify the date of their last menstrual period. If investigators deem necessary, urine pregnancy testing may be performed before enrollment in the study.

The planned enrollment demographics for our study are derived from the demographic representation of the Greater Boston area (U.S. Bureau of the Census, 2000), from which the majority of our human subjects will be drawn. We thus expect to enroll approximately 10% Hispanic or Latino subjects and 90% non-Hispanic/Latino. Among racial categories, we expect to enroll approximately 75% white subjects, 10% black or African-American, and <5% each American Indian/Alaska native, Asian, and Native Hawaiian or Other Pacific Islander. No sex/gender or racial/ethnic groups will be excluded from this study.

Our subject selection criteria are based purely on age (18-64); diagnosis of MTLE; and nonfulfillment of specific exclusion criteria. MTLE appears to be evenly distributed across racial/ethnic lines. One of our exclusion criteria is pregnancy (due to lack of definitive information on fetal safety in MRI), but we do not believe this will independently affect the sex/gender composition of our enrolled subjects in any significant way.

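### The optional second rTMS course is assigned by investigator choice, not at random, so its stated evidence on relative efficacy needs a random allocation rule for sham-group returnees or a narrower claim

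*Combined protocol and SAP*

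**What the plan says.** **Allocation.** B3.A, Subject Enrollment: "At the time of consent, randomization will occur based on order of enrollment into the study using a computer-generated randomization table". B3.C repeats the use of the table. Nothing describes a second randomization.

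**Entry to the second course.** B3.A, Follow-Up: "Investigators may invite subjects back to repeat the study procedures 2-7". Those invited may accept or decline.

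**Choice of protocol.** The same section states: "The follow-up rTMS protocol chosen by investigators will depend on the subject's response, or lack thereof, to the previously performed protocol". Its rTMS step opens "Based on analyses of the subject's response to the initially assigned rTMS protocol, the alternative protocol", then names low-frequency stimulation of correlated cortex or high-frequency stimulation of anti-correlated cortex. The last subsection of B2 adds that comparing alternate protocols within an individual may depend on brain connectivity.

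**Group 3.** "Group 3 will receive sham TMS as a control intervention". It is neither excluded from the second course nor given a rule of its own. B3.C excludes people with "prior brain surgery or exposure to TMS", so sham returnees would be the only subjects in the second course with no earlier active stimulation.

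**Analysis and claim.** B3.A, Additional Follow-Up Analyses, compares seizure and IED frequency after the second course with the pre-rTMS baseline and with the measures after the first course. B3.B, Data Analysis, says this analysis "will provide further evidence of the relative efficacy of the two rTMS protocols in downmodulating cortical excitability".

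**The concern.** A statement about relative efficacy needs a comparison of the two active protocols in which allocation is unrelated to expected outcome. In the second course, who returns and, for sham returnees, which protocol they get are both decided after the first-course response is known. Seizure counts fluctuate, so a choice made on a good or poor 12-week count is partly a choice on chance, and the later count tends to move back. A difference between protocols could then reflect the reasons for the choice.

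At stake is the standing of the second-course evidence on which active protocol is better. A reader of the final report could take it as support for the randomized Group 1 versus Group 2 result when it does not have that quality.

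**Working it through.** The plan gives no figure for the second course. Its one sample-size figure, 27 in total, concerns the first course. It reproduces as a repeated-measures ANOVA between-factors test with 3 groups, 2 measurements, f = 0.56, alpha 0.05 and an assumed correlation of 0.5 (N = 27, power 0.813). The point here uses only the planned 30 subjects in three equal groups: 30/3 = 10 per group.

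**1. Who gets what in the second course**

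| First course | Second course | How the protocol is set |
|---|---|---|
| Group 1, low-frequency | High-frequency, on the natural reading | Order follows the first randomization; return is by invitation after response |
| Group 2, high-frequency | Low-frequency, on the natural reading | As above |
| Group 3, sham | Either active protocol, by inference | Investigator choice after response, possibly also connectivity |

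**2. What each row can support**

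- Groups 1 and 2: within either group, second course minus first course mixes protocol with period. Taking both groups together could separate the two, but no such model is stated. Selection on response would cancel only if invitation worked alike in both groups.
- Group 3: free of earlier active stimulation, but low versus high is confounded with the reasons for the choice.

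**3. Carry-over**

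A 12-week follow-up diary and a new 12-week baseline diary lie between the courses, so they are at least 12 + 12 = 24 weeks apart. B3.B reports prior seizure reductions lasting at least eight weeks, which is a lower bound. Carry-over is possible but not shown.

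**4. What randomizing Group 3 returnees would add**

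The SE of a difference in means, in SD units, is sqrt(1/n1 + 1/n2), assuming equal SD. Group 3 is not in the first-course low versus high contrast, so combining the two contrasts stratified by course counts nobody twice.

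- First course alone, 10 v 10: sqrt(2/10) = 0.447.
- All 10 return, 5:5: information 5 + 2.5 = 7.5; SE = 1/sqrt(7.5) = 0.365, the same as 15 v 15. Ratio 0.816, so 18% smaller, with 50% more information.
- Five return, 3:2: information 5 + 1/(1/3 + 1/2) = 5 + 1.2 = 6.2; SE = 1/sqrt(6.2), about 0.40. This is about 10% smaller.
- 5 v 5 alone: a two-sided t-test at alpha 0.05 has power 0.20 at d = 0.8. For 10 v 10 it is 0.395. The value is in the combination.

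**5. Illustration of the possible bias (all parameters assumed)**

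Ten sham returnees were simulated 6,000 times per setting, with no true difference between protocols. Counts over 12 weeks were overdispersed, with means of 1, 2 or 4 seizures per 4 weeks before a floor of 1. The better half of sham responders got one protocol and the rest the other. The groups were compared by t-test on log count ratios at a nominal 5%.

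| Change measured from | Type I error, choice by response | Spurious ratio | Type I error, random |
|---|---|---|---|
| Original baseline | 0.188 to 0.201 | 0.44 to 0.47 | 0.045 to 0.050 |
| Post-first-course measure | 0.192 to 0.206 | 2.13 to 2.37 | 0.045 to 0.051 |
| Fresh second baseline | 0.044 to 0.052 | 0.99 to 1.02 | 0.048 to 0.051 |

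The inflation appears when the comparator is the original baseline, which also fed the choice, or the first-course follow-up measure. The second of these is a planned comparator. The first is one reading of the pre-rTMS baseline in Additional Follow-Up Analyses.

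**The case against.** The strongest reply is that the plan never sets up a low versus high contrast among sham returnees. B2 and Additional Follow-Up Analyses describe comparisons within the same individual, so the evidence is meant to come mainly from people who receive both active protocols, and for them the order was randomized. Group 3 returnees are not named anywhere, and a single alternative protocol fits a subject who has had one of the two active ones. The extension is optional and is said to give only further evidence. A fresh second baseline removed the inflation in the simple model above.

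Much of this stands. A reader might infer that the relative-efficacy statement rests on a sham-returnee contrast; the documents do not say so. A reader might also infer that carry-over biases the second course; with at least 24 weeks between courses that is not established. The simulated inflation applies to a contrast that the plan does not specify.

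What the reply leaves untouched is that return is selected on response in every group, that period is not addressed, that Group 3 has no stated rule although nothing keeps it out, and that the claim in B3.B carries no qualification. A fresh baseline also does not deal with a choice made on connectivity or preference; that effect was not quantified.

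**Conclusion.** The point holds as a minor one with a cheap improvement. As written, the second course yields response-selected, non-randomized data on the two active protocols, and B3.B presents them as further evidence of relative efficacy without saying so. The reading of Group 3 is an inference from a general rule with no exception.

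It would be wrong to conclude that the trial's randomized comparison is compromised. The first-course Group 1 versus Group 2 contrast and both main outcomes are untouched.

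The gain from randomizing sham returnees is at best a fall in SE from 0.447 to 0.365 SD, and to about 0.40 SD with 5 returnees. This assumes equal SD and no effect of prior sham. The best case also needs every Group 3 subject to be invited and to accept. The number who will return is not in the documents.

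**What to change.** Reconcile the last subsection of B2, B3.A Follow-Up and B3.B Data Analysis so that they give one rule for how the second-course protocol is assigned, including for Group 3.

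- **Allocation.** Where a returning Group 3 subject is, in the investigators' judgment, suitable for either of the two protocols already in the study, allocate between them 1:1 from the computer-generated table, after the subject has agreed to return.
- **Analysis.** For these subjects, analyse change from their own second 12-week baseline and combine it with the first-course low versus high contrast, stratified by course. Report the second courses of Groups 1 and 2 descriptively.
- **Fallback.** If investigators keep the choice, limit the B3.B sentence to exploratory description.

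The cost is a few lines of text and one more column in the randomization table, with no added subjects or procedures. The downside is that investigators give up discretion over the protocol for sham-group returnees. The fallback costs only a change of wording.

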The optimal rTMS protocol to achieve a reduction in brain hyperexcitability has not been determined

While low-frequency rTMS is known to decrease local cortical excitability, high-frequency rTMS increases such excitability. Low-frequency rTMS has had mixed results in clinical epilepsy trials, but dramatic improvement has been seen in patients with accessible cortical foci.^{5,4} When rTMS is used in medication-refractory depression, high-frequency rTMS is typically used for the left DLPFC, while low-frequency rTMS is used for the right DLPFC as an alternative option. Based on our preliminary data with rTMS in PNH and in normal individuals, we hypothesize similarly that using differential rTMS protocols for different cortical targets in MTLE, identified based on the nature of their connectivity to the epileptogenic mesial temporal lobe, will successfully downmodulate hyperexcitability in MTL circuits and thus treat the epileptic state.

Alternate rTMS protocols may be directly compared in some individuals to determine their effect on

brain hyperexcitability

In some individuals, the brain excitability data acquired after a particular rTMS protocol may be compared directly to the data acquired after an alternate rTMS protocol in the same individuals, depending on brain connectivity, thus allowing for additional information on the intraindividual variability of response to rTMS.

B3. DESCRIPTION OF RESEARCH PROTOCOL

A. Study Design – Overview, Methods, Procedures

Overview

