EEG recording of interictal epileptiform discharge (IED) frequency will occur 12 weeks after the last rTMS session. **Subject time: 1 hour.**

Additional Follow-Up Analyses

At 12-week follow-up after the second rTMS protocol, the primary outcome measure will be seizure frequency and the secondary outcome measure will be IED frequency. Both of those measures will be compared both to the pre-rTMS baseline and to the measures following the initial rTMS protocol. Subjects will be blinded to their group assignment, as will the investigator who reviews seizure diaries and determines IED frequency on EEG. Adverse events will be tracked closely throughout the study protocol.

Details of methods to be used

Brain image acquisition

Thirty subjects with MTLE will be imaged on a dedicated research 3.0-Tesla magnet (General Electric Signa VH/i, GE Healthcare, Waukesha, WI) with a commercial head coil. High resolution structural whole-brain images will be acquired using a T1-weighted sequence with 128 slices per slab, a 256 x 256 matrix, a field of view (FOV) of 256 mm, a slice thickness of 1.33 mm with 0.63 mm interslice gap, repetition time (TR) of 2530 ms, inversion time of 1100 ms, echo time (TE) of 3.39 ms, and flip angle of 7 degrees. Resting-state functional image acquisition will be performed while subjects are asked to rest quietly (acquisition time 6.4 min), using an echo-planar sequence sensitive to BOLD contrast with TR 6000 ms, TE 30 ms, FOV 256 mm, voxel size 2.0 x 2.0 x 2.0 mm, and flip angle 90 degrees.

rTMS protocol

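### Second-course outcomes are compared with first-course measures that may have decided who returned, and with a baseline that is not identified

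*Combined protocol and SAP*

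**What the plan says.** All references are to the combined protocol and SAP.

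Under Follow-Up in section B3.A, investigators assess the response to the first course and "determine if the subject may be appropriate for further rTMS". They may then invite the subject back; no threshold is given. The choice of second protocol depends on the subject's "response, or lack thereof, to the previously performed protocol". It is one of the two active protocols: "either low-frequency rTMS to cortical regions that are highly correlated with the epileptogenic MTL or high-frequency rTMS to cortical regions" with high anti-correlation.

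Returners repeat the diary and the pre-rTMS EEG. The diary item has the same wording for the original and the repeated procedures: "Subjects will keep a baseline seizure diary for 12 weeks". A returner therefore has two pre-treatment baselines.

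Additional Follow-Up Analyses (B3.A) says of seizure and IED frequency after the second course: "Both of those measures will be compared both to the pre-rTMS baseline and to the measures following the initial rTMS protocol". It does not say which baseline. Data Analysis (B3.B) says that this part "will provide further evidence of the relative efficacy of the two rTMS protocols in downmodulating cortical excitability". The ANOVA under Sample Size Justification covers baseline and follow-up in the three randomized groups; no model is given for the second course.

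Section B2 gives another basis for a within-person comparison. Data after one protocol may be compared with data after "an alternate rTMS protocol in the same individuals, depending on brain connectivity".

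**The concern.** A patient judged to have responded poorly will, on average, have had a chance excess of seizures in the first follow-up and a chance deficit in the original baseline. Later counts drift back towards the patient's usual rate. The second course then looks better than the first and worse than the original baseline, though nothing has worked. If responders are the ones who return, both signs reverse.

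The two comparisons in Additional Follow-Up Analyses can therefore disagree in sign with no treatment effect, and either could be cited as the relative-efficacy evidence that Data Analysis promises. The second baseline is recorded after the response assessment and plays no part in it, so it matters which baseline is meant.

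**Working it through.** **Plan's own figure.** None exists for the second course. The stated sample size of 27 concerns the randomized first phase and has no bearing here.

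**Notation.** X1 = original baseline, Y1 = first follow-up, X2 = second baseline, Y2 = second follow-up. Each is a 12-week diary count.

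**Direction.** Write each log count as the patient's own level plus a period deviation e, with no treatment effect. If return depends on Y1 relative to X1, and periods vary independently:
- mean of (Y2 - Y1) among returners = -mean of e(Y1);
- mean of (Y2 - X1) among returners = -mean of e(X1);
- mean of (Y2 - X2) among returners = 0.

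Selecting poor responders makes e(Y1) positive and e(X1) negative, so the first two errors have opposite signs.

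**Inputs.** From the documents: 12-week diaries, and at least one seizure per 4 weeks at entry (section C, Subject Selection). Assumed, because the documents give neither variability nor a return rule: median 4 seizures per 4 weeks; between-patient log SD 0.6 to 1.2; extra period log SD 0 to 0.7; correlation between adjacent periods 0 to 0.8; Poisson counts. There were 300,000 simulated patients per scenario before the entry floor. Changes are ratios of mean counts.

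**False change with no treatment effect**

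| Who returns | Y2 vs Y1 | Y2 vs X1 | Y2 vs X2 |
|---|---|---|---|
| Less than 50% reduction | -1% to -18% | +1% to +33% | -3% to about 0% |
| No improvement | -8% to -28% | +10% to +67% | -6% to +1% |
| Mild mix (60% of not improved, 40% of improved) | about -2% to -8% | about +2% to +10% | not tabulated |
| Everyone | about 0% | about 0% | about 0% |

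For the less-than-50% rule, the error versus Y1 is only -1% to -2% when variation is purely Poisson.

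**Second model.** Gamma-distributed rates with mean 2, 4 or 8 per 4 weeks, independent periods and overdispersion 0 to 0.3 gave -1% to -19% and -9% to -25% versus Y1 for the first two rules. One scenario checks the arithmetic (mean 8, overdispersion 0.1, no-improvement returners): Y1/X1 = 1.51 and Y2/Y1 = 0.83, so Y2/X1 = 1.51 x 0.83 = 1.25, which matches the simulated +25%. With 30 randomized and a paired t test on log counts (an assumption; the plan names no test), the no-improvement rule gave false-positive rates of 0.28 to 0.33 versus Y1, 0.25 to 0.31 versus X1 and 0.04 to 0.05 versus X2. If return depends on the level of Y1 alone, this model gave -2% to -30% versus Y1 and 0% versus X1.

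**Low versus high, by sequence.** Groups 1 and 2 are randomized and cross to each other. The contrast is half the difference between the low-then-high and high-then-low sequences in log(Y2/Y1). With no effect and one return rule in both arms, it is within 0.3% of zero for the first two rules and for everyone. If everyone returns in one arm and only the first or second subset in the other, the false difference is 0.5% to 10% or 4% to 15%. For a true 56% difference (the size in Sample Size Justification, assumed here for high versus low), a common selective rule attenuates the estimate to about 50-53% or 46-52%.

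**The same contrast built on X2.** Let the high protocol have ratio 0.44 and the low protocol 1.0. Suppose 25% of the log effect remains in X2 and is gone by Y2.
- High-then-low: Y2/X2 = 1 / 0.44^0.25 = 1 / 0.814 = 1.23.
- Low-then-high: Y2/X2 = 0.44.
- Ratio 0.44 / 1.23 = 0.36, an apparent 64% difference.

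With 50% remaining: 1 / 0.663 = 1.51, and 0.44 / 1.51 = 0.29, an apparent 71%. Simulation gave 61-65% and 69-71%. X2 therefore exaggerates this contrast if a first-course effect is still fading.

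IED frequency was not computed.

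**The case against.** The strongest objection is that no return rule exists. The phrase about response or its absence governs which protocol is chosen; the invitation turns only on whether further rTMS may be appropriate. Responders and non-responders may both come back, and if both extremes return about equally the error falls to 0% to +4%. This stands: the point is conditional. A reader might infer that only non-responders return, or that the comparisons must show a false change. The documents support neither.

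Second, Follow-Up does not define response. Just before it, the outcomes are set against baseline, so change from baseline is the natural reading, but it is not stated. If response means follow-up level alone, the original-baseline error disappears (0% in the independent-period model); the second-versus-first error does not.

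Third, the unnamed baseline may already be the second one. That comparison would then be largely clean, and second-versus-first would still be exposed.

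Fourth, connectivity may govern, as section B2 suggests. If it alone decides, this selection need not arise. The two passages are not reconciled.

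Fifth, the randomized sequences offer a nearly unbiased contrast under the null. They do if one rule applies in both arms, but the plan neither commits to that contrast nor fixes a common rule. It is also imprecise: with 10 per arm before selection and no effect, 95% of estimates span -17% to +22% at best and -46% to +84% at worst.

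A reader might also put a size on the bias among sham-first returners. Their choice of protocol depends on response and they have no mirror sequence, so confounding is a fair worry. Any figure would need an allocation rule that the documents do not contain.

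**Conclusion.** The point holds conditionally. If return favours one direction of response, the within-subject second-versus-first comparison is biased with no treatment effect, by roughly 1% to 28% across the non-responder and mild mixed rules tried. If response is judged as change from baseline, the original-baseline comparison is biased the other way, by about 1% to 67%. Both vanish if return is unrelated to response. The sizes rest on assumed seizure-rate variability and return rules and apply to seizure counts only; for IED frequency the argument needs IED change to inform the response judgement.

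Severity is minor to moderate and confined to the optional second course. A reader might infer that the trial's main result is compromised. It is not: the randomized first-phase comparison does not depend on who returns.

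**What to change.** 1. In Additional Follow-Up Analyses, name the second 12-week baseline diary and second pre-rTMS EEG, both already scheduled, as comparators for within-subject second-course change. State that they limit regression to the mean but not a fading first-course effect. The durability cited in Data Analysis, "durable over at least eight weeks of follow-up", does not exclude such fading.
2. Treat comparisons with the post-first-course measures and the original baseline as descriptive.
3. In Data Analysis, label the second course exploratory and without concurrent control, and rest relative efficacy on the randomized first phase.
4. Base any second-course low-versus-high statement on the low-then-high versus high-then-low contrast, using the two follow-up periods and not the second baseline. Note that selective return attenuates a true difference. Show sham-first returners separately.
5. Reconcile section B2 (connectivity) with Follow-Up (response) as the basis for the second protocol; this review takes no position on which governs. Report numbers invited, declined and returned by first-phase group.

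The cost is edits to these sections and one small table, with no new visit or measurement. The downside is that a within-subject efficacy claim from the second course is given up.
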